4 (cont)			
If tocilizumab is not available, siltuximab (an anti-IL-6 monoclonal antibody) may be used in the management of CRS, following the criteria outlined in this table. The recommended dose of siltuximab is 11 mg/kg administered over 1 hour as an IV infusion, consistent with the prescribing information for the treatment of multicentric Castleman's disease (Sylvant Prescribing Information), and the CARTOX Working Group Guidelines for CRS management (Neelapu et al, 2018). Siltuximab may be repeated if needed, in the event that CRS recurs after a subsequent infusion of tarlatamab. Siltuximab may not be repeated in an individual subject who develops anaphylaxis to siltuximab, or gastrointestinal perforation after siltuximab. 
Monitor:
 
CRS symptoms including temperature, blood pressure, and pulse oximetryFluid status, maintain IVF as neededConsider chest X-ray and obtaining appropriate cultures to rule out infectionIf refractory hypotension (after 2 fluid boluses), consider ECHO 
Admit to intensive care unit for close clinical and vital sign monitoring per institutional guidelines.
		

Abbreviations and footnotes defined on last page of table.

Table 6-2. Tarlatamab Dose Modification Guidelines for Adverse Events

Grade	Interruption/Delay	Specific Management	Restart guidance	Permanent Discontinuation
Tumor Lysis Syndrome (TLS) – Grading according to Common Terminology Criteria for Adverse Events (CTCAE v5.0) (see Section 11.11.3)				
Present	Immediate interruption/delay until event has improved to grade ≤ 1	
TLS should be managed according to the local SOC and institutional guidelines.
 
• Resume only if successfully managed and improvement to \leq grade 1 in ≤ 14 days• Consult with Amgen medical monitor.• In case of infusion interruption, continue treatment with next schedule infusion, do not resume prior infusion or administer delayed infusion.• Monitoring: per Monitoring Guidance for first tarlatamab administration (Section 6.1.1)	
If subject missed more than 2 consecutive doses of tarlatamab
 
OR
 
In case of repeat TLS event, or life-threatening TLS, permanently discontinue tarlatamab.
	

Abbreviations and footnotes defined on last page of table.

Table 6-2. Tarlatamab Dose Modification Guidelines for Adverse Events

Grade	Interruption/Delay	Specific Management	Restart guidance	Permanent Discontinuation

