11.11.3 Tumor Lysis Syndrome

Common Terminology Criteria for Adverse Events (CTCAE) version 5.0 classifies tumor lysis syndrome (TLS) in grade 3 (present), grade 4 (life threatening consequences; urgent intervention indicated) and grade 5 (death). Cairo and Bishop developed a system for defining and grading TLS based on Hande-Garrow classification of laboratory or clinical TLS (Coiffier et al, 2008). In this trial, the Cairo-Bishop classification will be used to define presence of TLS, ie, presence of laboratory TLS (see [Table 11-9](#)) and clinical TLS. Final event grade will be assigned according to CTCAE version 5.0.

Based on the Cairo and Bishop system, laboratory TLS is defined as any 2 or more abnormal serum values present within 3 days before or 7 days after initiation of treatment in the setting of adequate hydration (with or without alkalinization) and use of a hypouricemic agent ([Table 11-9](#)).

Table 11-8. Cairo-Bishop Definition of Laboratory Tumor Lysis Syndrome

Element	Value	Change from baseline
Uric acid	$\geq 476 \mu\text{mol/L}$ or 8 mg/dL	25% increase
Potassium	$\geq 6.0 \text{ mmol/L}$ or 6 mg/L	25% increase
Phosphorus	$\geq 2.1 \text{ mmol/L}$ for children or $\geq 1.45 \text{ mol/L}$ for adults	25% increase
Calcium	$\leq 1.75 \text{ mmol/L}$	25% decrease

Note: Two or more laboratory changes within 3 days before or 7 days after cytotoxic therapy will constitute laboratory tumor lysis syndrome.

Clinical TLS requires the presence of laboratory TLS in addition to 1 or more of the following significant complications: renal insufficiency, cardiac arrhythmias/sudden death, and seizures.

Approval Signatures

Document Name: Protocol Amendment tarlatamab 20210004 4

Document Description: Tarlatamab 20210004 Protocol Amendment 4

Document Number: CLIN-000318238

Approval Date: 19 Jul 2024

Type of Study Protocol: Amendment

Protocol Amendment No.: 4

Document Approvals

Reason for Signing: Management	Name: [REDACTED] Date of Signature: 19-Jul-2024 13:04:36 GMT+0000
--------------------------------	----------------------------------------------------------------------

Summary of Protocol Changes

Protocol Amendment 4

19 July 2024

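### In Table 11-8 the two potassium limits for laboratory TLS contradict each other 39-fold, and the adult phosphorus limit appears in mol/L and needs checking against the original page

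*Protocol*

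**What the plan says.** Section 11.11.3 states that "the Cairo-Bishop classification will be used to define presence of TLS", while the final event grade follows CTCAE version 5.0. The laboratory rule is: "laboratory TLS is defined as any 2 or more abnormal serum values present within 3 days before or 7 days after initiation of treatment". The same sentence adds two background conditions, sufficient hydration and use of a urate-lowering drug. Clinical TLS needs laboratory TLS plus at least one complication (renal, cardiac or seizure).

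The limits stand in Table 11-8, quoted here with the typesetting code of the extracted text:

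- Uric acid: "\geq 476 \mu\text{mol/L}$ or 8 mg/dL"
- Potassium: "\geq 6.0 \text{ mmol/L}$ or 6 mg/L"
- Phosphorus: "\geq 2.1 \text{ mmol/L}$ for children or $\geq 1.45 \text{ mol/L}$ for adults"
- Calcium: a single limit of 1.75 mmol/L or below.

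Each row also has a 25% change from baseline. The text does not say whether the absolute value and the change are alternatives or are both required. Section 11.11.3 twice refers to Table 11-9 for these criteria. The table is numbered 11-8, and the protocol's list of tables contains no Table 11-9.

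The TLS row of Table 6-2 acts when TLS is present: "Immediate interruption/delay until event has improved". It then sets a 14-day limit for resuming tarlatamab, requires consultation with the medical monitor, and calls for permanent discontinuation on a repeat or life-threatening event.

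**The concern.** A table that gives a limit in two units implies that the two figures are the same quantity. The uric acid row meets that test and the potassium row does not. In the phosphorus cell the limit for children is in mmol/L and the limit for adults is in mol/L. Inclusion criterion 102 admits adults only, so the adult figure is the one that applies.

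What is at stake is a uniform safety definition. TLS is named in the benefit/risk section as a potential safety concern of tarlatamab, and its presence leads to interruption of treatment. Table 11-1 lists chemistry under local laboratories, and about 240 sites are planned. Each site therefore compares its own laboratory report with the printed limits. If a limit can be read two ways, or cannot be reached, the same results may be called TLS at one site and not at another.

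**Working it through.** **Inputs.** The limits are from Table 11-8. The documents give no molar masses. I assume the standard values: potassium 39.098, phosphorus 30.974 and uric acid 168.11 g/mol. Conversion: mmol/L = (mg/L) / molar mass.

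**1. Control row, uric acid.** 8 mg/dL = 80 mg/L. 80 / 168.11 = 0.4759 mmol/L = 475.9 µmol/L, against 476 printed. The row reproduces, so two units in one cell are meant as equivalents.

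**2. Potassium.**
- 6 mg/L: 6 / 39.098 = 0.153 mmol/L.
- 6.0 mmol/L: 6.0 × 39.098 = 234.6 mg/L.
- Ratio: 234.6 / 6 = 39.
- Reading mg/L as mg/dL does not help: 60 / 39.098 = 1.53 mmol/L, still not 6.0.

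To see what the mg/L figure would do, assume serum potassium anywhere from 1.5 to 8 mmol/L. That is 59 to 313 mg/L, or 10 to 52 times the printed 6 mg/L. An assumed normal range of 3.5 to 5.0 mmol/L is 137 to 195 mg/L. Every sample meets the figure.

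**3. Phosphorus, if the page does say mol/L.** 1.45 mol/L = 1,450 mmol/L. Against the paediatric limit in the same cell, 1,450 / 2.1 = 690. In mass, 1.45 × 30.974 = 44.9 g of phosphorus per litre of serum, which cannot occur.

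**4. Effect on the rule of two.** Four elements, each abnormal or not, give 2^4 = 16 patterns. I compared the call with what it would be if potassium and phosphorus were flagged correctly.

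| Reading | Over-called | Under-called |
|---|---|---|
| mg/L potassium always met; phosphorus judged on the mol/L value only, never met | uric acid alone; calcium alone | potassium + phosphorus |
| mg/L potassium always met; phosphorus still counts (through the 25% change, or because the page says mmol/L) | uric acid, phosphorus or calcium alone | none |
| mmol/L potassium used; phosphorus never met | none | phosphorus + any one other element |

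Each reading misclassifies 3 of 16 patterns. These are counts of combinations, not patient frequencies. The documents give no laboratory distributions.

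**5. If both columns are required.** The mg/L figure then makes potassium count on a 25% rise alone. For example, 3.6 × 1.25 = 4.5 mmol/L stays inside the assumed normal range. Adult phosphorus could not count at all if the unit is mol/L.

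**The case against.** Several objections have force.

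- **The phosphorus unit may be a reading artefact.** It rests on one letter in a table cell read from PDF, and the extracted text has letter-level errors elsewhere, including in the drug's name. This stands. A reader might infer that two of the four rows are certainly wrong. The documents as available support only one certain contradiction, potassium, and one to be checked. The potassium contradiction does not depend on a single letter, since mg/dL fails as well.
- **The potassium cell also holds a limit in mmol/L.** This stands. Over-calling arises only where the mg/L figure is applied literally, and nothing in the documents shows a site or system doing so.
- **Phosphorus may still count through the 25% increase.** This stands if the two columns are alternatives, which the protocol leaves unstated.
- **One extra abnormality would not by itself stop treatment.** A reader might infer that potassium is always abnormal, so any other deviation makes TLS and triggers Table 6-2. The section does not support so direct a chain. It sets the hydration and urate-lowering conditions, and Section 6.1.3.1 lists only dexamethasone and IV hydration around the tarlatamab infusion. It describes presence of TLS by naming both laboratory and clinical TLS, and clinical TLS needs a complication. Grading is by CTCAE, and restart needs the medical monitor. These checks weaken the chain. They do not make the two potassium figures agree.
- **No analysis is shown to depend on the table.** A reader might infer wrong edit checks or a wrong programmed TLS flag. The documents describe neither. The SAP's events of interest do not include TLS, and its laboratory section derives no TLS criterion. Adverse events come from investigator-completed forms.

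The publication cited for the definition cannot be consulted here, so only inconsistency within the protocol can be claimed.

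**Conclusion.** The point holds for potassium: the two figures in one cell of the trial's TLS definition differ 39-fold, and the lower one would be met by every sample. For adult phosphorus it is conditional. If the original page reads mol/L, the absolute limit is out of reach, and phosphorus could count only through the 25% change, provided the columns are alternatives.

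The consequence is possible misclassification of laboratory TLS in some patterns, 3 of 16 under each reading tabulated, in either direction depending on how a site reads the table. Sites using the mmol/L potassium limit avoid the over-calling. No count of patients or TLS events follows from the documents, and no efficacy endpoint, estimand or error rate is affected. The assumptions are the standard molar masses and, for the claim about every sample, a serum potassium of 1.5 to 8 mmol/L.

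This is more than a background typographical slip because the table defines an event on which treatment rules act.

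**What to change.** The sponsor should:

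1. reconcile the two potassium figures so that the row states a single limit, by deleting or recomputing the mg/L figure;
2. check the adult phosphorus unit against the original page and state it in the same unit as the paediatric value;
3. change the two references to Table 11-9 in Section 11.11.3 to Table 11-8.

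Which clinical threshold applies is for the sponsor to settle. The cost is one appendix table and two cross-references, by clarification memo or in the next amendment, with no added data or procedures.

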**Table of Abbreviations**

Term/Abbreviation	Definition/Explanation
AE	Adverse Event
AMQ	Amgen MedDRA Query
AST	Aspartate Aminotransferase
ASTCT	American Society for Transplantation and Cellular Therapy
ALP	Alkaline Phosphatase
ALT	Alanine Aminotransferase
CRS	Cytokine Release Syndrome
CTCAE	Common Terminology Criteria for Adverse Events
D	Day
ECG	Electrocardiogram
ECOG	Eastern Cooperative Oncology Group
EOI	Event of Interest
FDA	US Food and Drug Administration
eIV	Extended Intravenous
hr	Hour
ICANS	Immune Effector Cell-associated Neurotoxicity Syndrome
iSAP	Integrated Statistical Analysis Plan
ISS	Integrated Summary of Safety
KM	Kaplan-Meier

MedDRA	Medical Dictionary for Regulatory Activities
PA	Primary Analysis
PD-1	Programmed Death Protein 1
PD-L1	Programmed Death Protein 1 Ligand
Q3W	Every 3 Weeks
QTcB	Bazett-corrected QT Interval
QTcF	Fridericia-corrected QT Interval
RR	Respiratory Rate
SAP	Statistical Analysis Plan
SCLC	Small Cell Lung Cancer
SOC	System Organ Class
TEAE	Treatment-emergent Adverse Event
TRAE	Treatment-related Treatment-emergent Adverse Event
ULN	Upper Limit of Normal
WHO DRUG	World Health Organization Drug

## 1. INTRODUCTION

The objective of this Integrated Statistical Analysis Plan (iSAP) is to describe the analysis of Integrated Summary of Safety (ISS) that will be performed on all relevant safety data to support second-line tarlatamab filing.

Studies under the scope of ISS are:

- Monotherapy cohorts of 20160323 (Parts A, D, E, F and G) :  
A Phase 1 Study Evaluating the Safety, Tolerability, and Pharmacokinetics of Tarlatamab in Participants With Small Cell Lung Cancer.
- 20200491 (Parts 1, 2, 3):  
A Phase 2 Study Evaluating the Efficacy, Safety, Tolerability, and Pharmacokinetics of Tarlatamab in Participants with Relapsed/Refractory Small Cell Lung Cancer After Two or More Prior Lines of Treatment.
- Tarlatamab arm of 20210004:  
A Randomized, Open-label, Phase 3 Study of Tarlatamab Compared With Standard of Care in Participants With Relapsed Small Cell Lung Cancer After Platinum-based First-line Chemotherapy.

Safety data from study 20200491, monotherapy cohorts of study 20160323 and tarlatamab arm of study 20210004 will be integrated and analyzed. **If needed, additional studies may be added after data are available.**

Output headers are shown below:

**Table 1. Output Header**

Study 20160323	Studies 20210004, 20200491, and 20160323	Studies 20200491 and 20160323	Studies 20210004, 20200491, and 20160323
Tarlatamab < 10 mg (N = xx) n (%)	Tarlatamab 10 mg (N = xx) n (%)	Tarlatamab > 10 mg (N = xx) n (%)	Tarlatamab All Doses (N = xx) n (%)

D = Day; eIV = Extended IV; hr = Hour; Q3W = Every 3 weeks.

**Tarlatamab < 10 mg** includes study 20160323 cohorts 1-7. **Tarlatamab 10 mg** includes study 20210004 1->10 mg; study 20200491 1->10 mg (part 1 randomized arm, part 2, and part 3); study 20160323 cohorts 8, 32 and 35. **Tarlatamab > 10 mg** includes study 20200491 1->100 mg (part 1 randomized arm); study 20160323 cohort 9 (1->30 mg), cohorts 10, 30, (1->100 mg), cohort 11 (tarlatamab + dexamethasone), cohort 34 (1->100 mg 24-hr outpatient), cohorts 26 (■)

mg eIV-[redacted] mg), cohorts 27 and 31 ([redacted] mg eIV-[redacted] mg), 2-step dosing cohort 23 ([redacted] mg), cohort 37 ([redacted] mg Q3W 21 day/cycle), and cohort 38 ([redacted] mg D1/D8 21 day/cycle). **Tarlatamab All Doses** includes all participants who receive any dose of tarlatamab monotherapy from studies 20210004, 20200491, and 20160323.

In addition, Cytokine Release Syndrome (CRS) data from study 20200491, monotherapy cohorts of study 20160323 and tarlatamab arm of study 20210004 will be integrated and analyzed for participants who received tarlatamab and were enrolled from monotherapy cohorts of study 20160323 part F and tarlatamab arm of study 20210004 under PA3 with mandatory 6 to 8 hours monitoring post-infusion at cycle 1 day 1 and cycle 1 day 8 and participants who received tarlatamab with more than mandatory 6 to 8 hours monitoring post-infusion at cycle 1 day 1 and cycle 1 day 8 may. Output headers are shown below:

**Table 2. Output Header for 6 to 8 Hours Cohorts**

Studies 20210004, 20200491, and 20160323, More Than 6 to 8 Hours Monitoring	Studies 20210004 and 20160323, With 6 to 8 Hours Monitoring	Study 20160323, With 6 to 8 Hours Monitoring	Study 20210004, With 6 to 8 Hours Monitoring	Study 20210004, More Than 6 to 8 Hours Monitoring	Overall
Tarlatamab 10 mg (N = xx) n (%)	Tarlatamab 10 mg (N = xx) n (%)	Tarlatamab 10 mg (N = xx) n (%)	Tarlatamab 10 mg (N = xx) n (%)	Tarlatamab 10 mg (N = xx) n (%)	Tarlatamab 10 mg (N = xx) n (%)

**Studies 20210004, 20200491, and 20160323, more than 6 to 8 hours monitoring** includes participants who receive 10 mg of tarlatamab monotherapy from studies 20210004, 20200491, and 20160323 and were monitored for more than 6 to 8 hours. **Studies 20210004 and 20160323, with 6 to 8 hours monitoring** includes study 20210004 under protocol amendment 3 with mandatory 6 to 8 hours monitoring post-infusion at cycle 1 day 1 and cycle 1 day 8 and study 20160323 part F. **Study 20160323, with 6 to 8 hours monitoring** includes study 20160323 part F. **Study 20210004, with 6 to 8 hours monitoring** includes study 20210004 under protocol amendment 3 with mandatory 6 to 8 hours monitoring post-infusion at cycle 1 day 1 and cycle 1 day 8. **Study 20210004, more than 6 to 8 hours monitoring** includes participants who receive 10 mg of tarlatamab monotherapy from study 20210004 and were monitored for more than 6 to 8 hours. **Overall** includes all participants who received 10 mg of tarlatamab monotherapy from studies 20210004, 20200491, and 20160323, regardless of monitoring period.

## 2. OBJECTIVES

The safety profile of tarlatamab will be evaluated through various analyses including, but not limited to, a description of overall exposure to tarlatamab, summaries of Treatment-

emergent Adverse Events (TEAEs), treatment-related TEAEs (TRAEs), electrocardiogram (ECG), clinical laboratory tests, physical measurements and vital signs.

### 3. DEFINITIONS

#### Baseline

For any variable, unless otherwise specified, the baseline is the last nonmissing assessment taken prior to the first administration of tarlatamab treatment or other protocol-required therapies. Where baseline measurements are taken on the same day as the tarlatamab administered and no times are present, it will be assumed that these measurements are taken prior to the study specified treatment being administered.

For parameters/assessments not scheduled to be performed (or scheduled but not performed) on the same day as the earliest date of first administration of tarlatamab or other protocol-required therapies, the baseline value is the value from the screening period measured closest to the earliest date of first administration of tarlatamab or other protocol-required therapies. In the event that multiple assessments are done on the same day as the earliest date of first administration of tarlatamab or other protocol-required therapies and there is no time associated with the assessments, the value associated with the last clinically planned event before the earliest date of first administration of tarlatamab or other protocol-required therapies will be used as the baseline value.

#### Baseline ECG

Baseline ECG is the cycle 1 day 1 pre-dose assessment.

- If multiple ECGs are available, the mean of all ECGs will be calculated for baseline.
- If only one ECG is available, this assessment will be used.

If cycle 1 day 1 pre-dose ECG assessment is missing, the last nonmissing assessment taken prior to the first administration of tarlatamab treatment will be used as the baseline ECG. If multiple nonmissing assessments are available at the same date, the mean of all assessments will be used as baseline ECG.

#### Postbaseline ECG

The calculation follows the same rule as the baseline ECG.

**Bazett-corrected QT Interval (QTcB)**

The Bazett correction will be calculated from the investigator reported QT (msec) and RR interval (msec) if available, as follows:

$$QTcB = QT / (RR/1000)^{0.5}$$

QTcB will be only summarized if RR is collected.

**Change from Baseline**

Change from baseline is the arithmetic difference between post-dose assessments and baseline assessment.

$$\text{Change (absolute) from baseline} = \text{postbaseline value} - \text{baseline value}$$

**Duration of Adverse Event**

$$\text{Duration of resolved adverse events (days)} = (\text{event end date} - \text{event start date}) + 1$$

